Cover page

Official Project Title: Reducing Pesticide Exposures in Child Care Centers

NCT # 03319927

Document: **Statistical Analysis**

Plan Document Date 8/13/2025

Statistical Analysis Plan

Frequency tables for all the variables and measures of central tendency and variability for continuous variables were stratified by randomization group to check for imbalances. If the two groups differ significantly at baseline on covariates, we will use methods based on the Rubin causal model (e.g., propensity scores, double-robust estimation) to obtain the desired population-level estimates under the counterfactual assumption of balanced groups. (Luellen, Shadish, & Clark, 2005; Rubin, 2004; Seaman & Copas, 2009; Shadish, Luellen, & Clark, 2006; Weitzen, Lapane, Toledano, Hume, & Mor, 2004) Descriptive analyses will also yield important information about the child care centers' levels of pesticide contamination and child exposures; these data were summarized by group, time, and cohort. Primary inferential analyses were performed using tobit regression models which provided an approach for modeling repeatedly measured and clustered dependent variables in this study. (Verbeke & Molenberghs, 2000) SAS (SAS Institute, 2002). Survey and observational data were analyzed using parametric or non-parametric statistics based on the distribution of the dependent variable aggregated by child care center (n=85). All tests used a priori $p < .05$ as level of statistical significance.

Specific Aim 1. To determine if a nurse-led IPM workshop improves child care center staff's IPM knowledge (a) **Unit of Analysis:** Child care staff aggregated by center. (b) **Dependent Variable:** IPM knowledge score. (d) **Independent Variables: Group and Time.** Paired ttests were conducted to assess change in knowledge at baseline and post-IPM workshop.

Specific Aim 2. To determine if an IPM intervention in child care centers (a) increases the number of IPM policies, (b) increases IPM practices, (c) decreases pest problems (i.e., number of pests present, pest debris), and (d) increases center director's self-efficacy. (a) **Unit of Analysis:** Child care centers. (b) **Dependent Variable:** IPM policy, IPM practices, pest problems, director self-efficacy. (c) **Independent Variables: Group and Time.** Normally distributed dependent variables were analyzed using ttests or ANOVA and non-normally distributed dependent variables were analyzed using Kruskal-Wallis tests.

Specific Aim 3: To determine if an IPM intervention reduces pesticide contamination in the intervention IPM child care centers compared to the PA control centers. (a) **Unit of Analysis:** Child care centers. (b) **Dependent Variable:** Pesticide concentrations in dust. (c) **Independent Variables: Group, Time, and Cohort.** Tobit regression models were conducted with an additional random intercept term for child care center to account for correlations within centers across timepoints (baseline, post-intervention). The concentrations and detection of the 15 pesticides measured in dust were analyzed separately using the STATA command 'tobit'.

Specific Aim 4: To determine if an IPM intervention reduces children's exposure to pesticides in the IPM intervention child care centers compared to the children in the PA control centers. (a) **Unit of Analysis:** Enrolled children with complete wristband data at baseline and post-intervention aggregated by child care center. (b) **Dependent Variable:** Pesticides measured in children's wristbands worn at the child care. (c) **Independent Variables: Group, Time, and Cohort.** Pesticide concentrations analyzed in the silicone wristbands. (c) **Independent Variables: Group, Time, and Cohort.** Tobit regression models were conducted with an

additional random intercept term for child care center to account for correlations within centers across timepoints (baseline, post-intervention). The concentrations and detection of the 13 pesticides measured in dust were analyzed separately.

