A randomized control study will be conducted and include 90 child care centers in four CA counties enrolled in five 9-month cycles over five years. The counties will be matched on rates of poverty, number of children under age five, and annual pesticide usage. The matched counties will be randomly assigned to an IPM intervention or an active control intervention (i.e. physical activity). During the 7-month Intervention phase, trained child care health consultants will host one workshop per center on the intervention topic (IPM or physical activity) and conduct seven monthly consultations per center starting with the center director and the child care health consultant setting center-specific goals.

The 'Follow-Up Study' will assess IPM practices, pests, and pesticides in all of the enrolled child care centers. The directors will complete surveys, the research staff will conduct observations, and a researcher will collect dust samples in the child care centers the same season and month as the baseline period.

BACKGROUND AND SIGNIFICANCE: Briefly provide the background and significance of this study (e.g. why is this study needed) (space limit: one page):

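### Covariate adjustment depends on a significance test of unnamed baseline covariates; it should be fixed in advance, chiefly for Aim 2, and the SAP should say whether the rule was triggered

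*SAP*

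**What the plan says.** The general methods paragraph of the SAP tabulates variables by arm to look for imbalance and then states: "If the two groups differ significantly at baseline on covariates, we will use methods based on the Rubin causal model". The methods are given as examples: "e.g., propensity scores, double-robust estimation) to obtain the desired population-level estimates under the counterfactual assumption of balanced groups". The same paragraph sets the threshold: "All tests used a priori $p < .05$ as level of statistical significance". No covariates are listed, nothing says how many must differ, and no single adjusted method is chosen.

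The default analyses differ by aim. For Aim 2 (policies, practices, pest problems, director self-efficacy) they are t-tests or ANOVA, or Kruskal-Wallis tests where the data are not normal, with Group and Time as the only independent variables. For Aims 3 and 4 the SAP gives "Independent Variables: Group, Time, and Cohort. Tobit regression models were conducted with an additional random intercept term for child care center", fitted to baseline and post-intervention values. A Group x Time interaction is not written out for any aim.

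Survey and observational data are analyzed as "aggregated by child care center (n=85"). The analyses are described in the past tense and the adjustment rule in the future tense. Neither document says whether the rule was triggered.

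**The concern.** A baseline p-value measures how surprising a difference is for the number of centers. It does not measure whether the covariate predicts the outcome, which is what decides whether an imbalance matters. A rule based on it can fail in two directions: it leaves moderate imbalances in a strong predictor unadjusted, and it fires on chance differences in covariates that do not matter.

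Two further points are at stake. The choice between unadjusted and adjusted estimates is made by the data, from an unlisted set of covariates and an open list of estimators. Also, the precision available from a prognostic baseline measure, which the trial collects in every center, is used in Aim 2 only if a test happens to be significant.

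**Working it through.** The documents give no power, effect-size or sample-size calculation, so there is no stated figure to reproduce. The check works out what the stated rule does.

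**Inputs.** From the SAP: 85 centers and a 0.05 level. Assumed, because not stated: two-sided tests; arms of 42 and 43 (30 and 55 as a range); covariate-outcome correlation 0.5 (range 0.3 to 0.7); 5 to 20 covariates.

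**1. Smallest difference that triggers adjustment.** In SD units, SE = sqrt(1/42 + 1/43) = 0.217. Threshold = t(0.975, 83) x SE = 1.989 x 0.217 = 0.43 SD. For 30 and 55 it is 0.45 SD. For a binary covariate near 50%, 1.96 x sqrt(0.25 x (1/42 + 1/43)) = 0.21, or 21 percentage points.

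**2. How often a real imbalance is missed.** The power of the baseline test is 28% for a true 0.3 SD difference and 45% for 0.4 SD, so they are missed 72% and 55% of the time.

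**3. What remains when a 0.3 SD imbalance is missed.** Missed cases have an observed difference between -0.4315 and 0.4315, so the mean must be taken within those limits (normal approximation):
- lower limit a = (-0.4315 - 0.3)/0.2169 = -3.37; upper limit b = (0.4315 - 0.3)/0.2169 = 0.606
- mean = 0.3 + 0.2169 x (0.0014 - 0.3320)/0.7274 = 0.3 - 0.099 = 0.20 SD
- bias in an unadjusted post-intervention comparison = correlation x 0.20 = 0.06, 0.10 and 0.14 outcome SD at correlations 0.3, 0.5 and 0.7

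**4. How often chance alone triggers the rule.** For k independent, balanced covariates, 1 - 0.95^k = 23%, 40% and 64% for k = 5, 10 and 20.

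**5. Effect on error rates and power.** A simulation (20,000 runs, 42 and 43 independent centers, one continuous covariate, ANCOVA standing in for the adjusted method) compared testing then adjusting with always adjusting:

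| Correlation | Type I, test then adjust | Type I, always adjust | Power at 0.5 SD, test then adjust | Power at 0.5 SD, always adjust |
|---|---|---|---|---|
| 0.3 | 4.7% | 4.8% | 63% | 66% |
| 0.5 | 4.5% | 5.1% | 63% | 74% |
| 0.7 | 3.8% | 5.0% | 64% | 89% |

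These figures illustrate the rule. They treat centers as independent and are not the trial's actual power.

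**6. Which aims are exposed.** Aim 2's default tests have no covariate terms, so steps 3 and 5 apply to them most directly. The Aim 3 and 4 models contain cohort, both time points and a center intercept. If the effect is the Group x Time term, additive imbalances that are stable over time largely cancel, and what remains is covariates that affect change.

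**The case against.** The strongest objection is that the SAP's primary inferential analyses, the tobit models, already hold cohort and the baseline measurement whatever the baseline tests show. That stands and confines the point mainly to Aim 2, although the SAP leaves the Group x Time term unstated. It is also fair that the covariate counts and correlations above are assumptions. The Protocol offers some protection by design: "The counties will be matched on rates of poverty, number of children under age five, and annual pesticide usage".

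Four stronger readings are tempting but not supported.
- *The rule produces false positives.* In the simulation with independent centers the overall type I error was 3.8 to 4.7%, so it was not inflated.
- *A 0.3 SD imbalance leaves 0.15 SD of bias* (0.3 x 0.5). The cases that escape the test have smaller observed differences, averaging 0.20 SD, so the figure is about 0.10 SD.
- *The trigger replaces the whole analysis.* The SAP does not say that propensity or doubly robust methods displace the tobit models; they could be combined.
- *Propensity methods must fail for lack of overlap because counties were assigned.* The SAP does not say that county-level covariates would enter the propensity model. Confounding of county with arm comes from the design, in which "The matched counties will be randomly assigned to an IPM intervention or an active control intervention" and there are four counties. It exists with or without this trigger.

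**Conclusion.** The point holds in a limited form. The SAP lets a 0.05-level test on unnamed covariates decide whether adjustment is used, and neither document overrides this. For 42 and 43 centers the rule ignores observed differences below about 0.43 SD and misses a true 0.3 SD imbalance 72% of the time. The average bias left in those cases is about 0.10 outcome SD at an assumed correlation of 0.5, for an unadjusted post-intervention comparison. Ten independent, balanced covariates would set it off by chance 40% of the time.

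The consequences are lost precision, conditional bias and room for analytic choice, chiefly in Aim 2. For Aims 3 and 4 the remaining need is to state the effect term. Because the rule's outcome is not reported, a reader cannot tell which estimator lies behind the results.

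**What to change.** Delete the significance trigger and replace it with the following.

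- **Aim 2:** a center-level model of each post-intervention outcome, adjusted for its baseline value and cohort whatever the baseline p-values. Where the outcome is not normal, use rank-based, ordinal or count regression, since a Kruskal-Wallis test cannot take covariates.
- **Aims 3 and 4:** state that the effect is the Group x Time term, with cohort retained.
- **Baseline balance:** describe it with standardized differences, without tests.
- **Propensity-score or doubly robust estimation:** keep one named method, as a sensitivity analysis.
- **Disclosure:** state whether the trigger fired and on which covariates, show adjusted and unadjusted results side by side, and label the revised models as specified after the fact.

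The cost is more than wording: the Aim 2 t-tests and rank tests give way to models, and some analyses must be rerun. The baseline outcome measures and cohort are already available. None of this removes the confounding of county with arm.

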Cover page

Official Project Title: Reducing Pesticide Exposures in Child Care Centers

NCT # 03319927

Document: Study Protocol

Document Date: 8/13/2025

Study Protocol

UCSF IRB Study Application Section 8.0

8.2 HYPOTHESIS: Describe the hypothesis or what the study hopes to prove (Help Text updated 9/13):

1. Child care center staff who attend the IPM workshop will have significantly increased knowledge of IPM and hazards of pesticide use compared to their pre-workshop knowledge and compared to the control center staff.
- 2.: Post-intervention, the IPM intervention child care centers will have (a) higher numbers of written IPM policies, (b) more IPM practices, (c) fewer pest problems, and (d) higher director self-efficacy for pest management compared to pre-intervention and compared to the control centers.
3. Post-intervention, the IPM intervention child care centers will have lower concentrations and loadings of pesticides in dust compared to pre-intervention and compared to the control centers.
4. Post-intervention, children's personal exposure to pesticides, as measured by silicone wristbands, will be lower compared to pre-intervention and compared to that of children in the control centers.

8.3 AIMS: List the specific aims:

1. To determine if a nurse-led IPM workshop improves child care center staff's IPM knowledge.
2. To determine if an IPM intervention in child care centers (a) increases the number of IPM policies, (b) increases IPM practices, (c) decreases pest problems (i.e., number of pests present, pest debris), and (d) increases director's self-efficacy.

3. To determine if an IPM intervention reduces pesticide contamination in the intervention child care centers compared to the control centers.
4. To determine if an IPM intervention reduces children's and teachers' exposure to pesticides in the intervention child care centers compared to the children in the control centers.

8.4 DESIGN: Briefly describe the study design (e.g., observational, interventional, randomized, placebo-controlled, blinded, cross-over, cross-sectional, longitudinal, pharmacokinetic, etc.):

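### Aims 3 and 4 test 15 dust and 13 wristband pesticides separately at p < .05 with no multiplicity control, so each aim's chance of a false reduction is well above the nominal level

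*SAP*

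**What the plan says.** The opening paragraph of the SAP gives the only significance rule: "All tests used a priori $p < .05$ as level of statistical significance". For Aim 3 it states "The concentrations and detection of the 15 pesticides measured in dust were analyzed separately", using tobit models with a random intercept for center. Aim 4 has a matching sentence, "The concentrations and detection of the 13 pesticides measured in dust were analyzed separately". That sentence says dust, but the dependent variable given for Aim 4 is "Pesticides measured in children's wristbands worn at the child care", so I read the 13 as wristband analytes.

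The word primary appears in the SAP only in "Primary inferential analyses were performed using tobit regression models", which identifies a type of model and not an outcome. Neither document gives a primary pesticide, a summed or composite measure, an order of testing, or a family-wise or false-discovery correction. Neither says how many significant pesticides, or which, would count as a reduction.

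The protocol's hypotheses (section 8.2) are single statements. Hypothesis 3 expects "lower concentrations and loadings of pesticides in dust compared to pre-intervention and compared to the control centers"; Hypothesis 4 expects lower personal exposure in children, measured by wristband.

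**The concern.** Each hypothesis is one claim, but it is examined through 15 or 13 separate models, each allowed its own 5% error. With no rule linking those results to the claim, .05 describes a single pesticide. It does not describe the error rate of a statement that the intervention reduces contamination or exposure. A report could present one or two nominally significant pesticides as support for the aim, and the plan gives a reader no means of telling how surprising that would be if the intervention did nothing.

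**Working it through.** The documents give no family-wise error, power or sample-size calculation, so there is no figure of theirs to reproduce.

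**Inputs from the documents**
- Level per test: .05 (SAP, opening paragraph).
- Number of pesticides: m = 15 (Aim 3) and m = 13 (Aim 4).

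**Assumptions, because the documents are silent**
- Tests are two-sided, so a false result in the direction of reduction has probability .05/2 = .025 per pesticide.
- Each test has true size 5%.
- The correlation ρ between pesticide test statistics is unknown; 0 to 0.9 is shown.
- One concentration test per pesticide. Detection is added at the end.

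**Step 1. Independence, no true effect**

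At least one false reduction, 1 − 0.975^m:
- Dust: 1 − 0.975^15 = 0.316
- Wristbands: 1 − 0.975^13 = 0.280

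At least one false positive in either direction, 1 − 0.95^m:
- Dust: 1 − 0.95^15 = 0.537
- Wristbands: 1 − 0.95^13 = 0.487

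Expected false reductions: 15 × .025 = 0.375 and 13 × .025 = 0.325. These counts do not depend on the correlation, but they do depend on each test having its stated size.

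If the tests were one-sided at .05, the false-reduction figures would be the 53.7% and 48.7% above.

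**Step 2. Positive correlation**

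For equally correlated normal test statistics with c = 1.96, the chance of at least one false reduction is

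1 − ∫ Φ[(c − √ρ·u)/√(1 − ρ)]^m φ(u) du.

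| ρ | Dust, m = 15 | Wristbands, m = 13 |
|---|---|---|
| 0 | 31.6% | 28.0% |
| 0.1 | 28.9% | 25.9% |
| 0.3 | 23.5% | 21.4% |
| 0.5 | 18.1% | 16.7% |
| 0.7 | 12.8% | 12.0% |
| 0.9 | 7.2% | 6.9% |

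The reference value for one two-sided test is 2.5%. Every entry exceeds it.

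**Step 3. If detection is tested as well**

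The count becomes 30 and 26. Independence would give 1 − 0.975^30 = 53.2% and 1 − 0.975^26 = 48.2%, but these are too high because detection and concentration come from the same measurement. With each concentration/detection pair correlated 0.5 to 0.9, and pesticides independent of one another, the chance of at least one false reduction is 50% to 42% for dust and 45% to 37% for wristbands. Correlation between pesticides would lower these too.

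**Step 4. Effect of the correction**

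Benjamini-Hochberg ranks the m p-values and compares the k-th smallest with k × .05/m. A pesticide that is significant alone needs p ≤ .05/15 = .0033 (dust) or .05/13 = .0038 (wristbands). When no pesticide is affected, the false discovery rate equals the chance of any false positive. Under independence the 53.7% and 48.7% of Step 1 therefore come down to 5% within each aim.

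**The case against.** A reader might add the two aims together and count detection, giving 28 or 56 tests and a 76% or 94% chance of a false positive, and conclude that a false reduction is likely. The documents do not support that reading, for three reasons. Those percentages count errors in both directions. They pool two aims that the protocol states as separate hypotheses. The 94% also treats detection as independent of concentration. Whether detection is tested at all is unclear: the Aim 3 dependent variable is concentration, the command is tobit, which handles non-detects as censored values, and no detection model is given.

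It can also be said that analysing pesticides one by one suits the study. The protocol's background section prefers wristbands to class-level biomarkers because they give pesticide-specific information. This stands as a reason to keep the individual models. It does not justify leaving their p-values uncorrected when the hypothesis is a single claim.

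A composite primary outcome is open to dispute. Averaging log concentrations needs a value for each non-detect, which tobit avoids. Much of the SAP is in the past tense, so a composite named primary now could not be presented as prespecified. Both points stand, so a composite is not the core remedy here.

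The 5% size is itself an assumption. The protocol randomises counties, whereas the SAP's models carry a random intercept only for center. If county clustering matters, the true size may differ from 5%, probably upward.

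Finally, the documents do not say that one significant pesticide would be taken as success. They state no decision rule at all, so the risk is one the plan leaves open and not a misuse it prescribes. Nor do they call these analyses exploratory: the hypotheses are directional and the tobit models are called the primary inference. The year 1 preliminary dust result in section 8.6, which showed no significant decreases, does not control error in the full analysis.

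**Conclusion.** The concern holds for each aim taken separately. With two-sided tests of true size 5%, concentration only and no real effect, the chance of at least one false reduction is at most about 32% (dust) and 28% (wristbands), reached under independence. At a correlation of 0.7 it is about 13% and 12%. A single test carries 2.5%. The chance of any false positive in either direction is 54% and 49% under independence. The correlation is not given in the documents, so the range should be quoted with the figures. That the error exceeds nominal is secure across the whole range; that a false reduction is more likely than not is not. The point should be corrected, but it does not invalidate the individual models.

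**What to change.** In the SAP's opening paragraph and under Aims 3 and 4, replace the blanket .05 for individual pesticides with Benjamini-Hochberg control at 5%, applied within the 15 dust pesticides and, separately, within the 13 wristband pesticides. State whether tests are two-sided. Report all 15 and all 13 Group x Time estimates with confidence intervals whatever their significance. Say whether detection is modelled and how, and label any such analysis supportive.

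Optionally, add one joint censored (tobit-type) model per aim with a Group x Time effect common to all pesticides. It addresses the single-claim hypothesis directly and needs no imputation of non-detects. If results are already known, label it post hoc.

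The core change needs wording and a re-ranking of p-values, with no new data; the optional part adds one model per aim. The price is that some single-pesticide results may lose nominal significance.

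### SAP Aim 1 names only a within-arm paired t-test, so the control half of Hypothesis 1 has no named test; Aim 2 leaves its between-arm contrast unspecified.

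*SAP*

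**What the plan says.** Protocol 8.2, Hypothesis 1, expects staff at IPM centers to show "significantly increased knowledge of IPM and hazards of pesticide use compared to their pre-workshop knowledge and compared to the control center staff". These are two contrasts: one within the IPM arm over time and one between arms. Hypothesis 2 has the same two-part form for policies, practices, pest problems and, in its last item, "higher director self-efficacy for pest management compared to pre-intervention and compared to the control centers".

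Under Specific Aim 1 the SAP gives "Independent Variables: Group and Time" and then one analysis: "Paired ttests were conducted to assess change in knowledge at baseline and post-IPM workshop". Under Specific Aim 2 it lists the same two variables and states: "Normally distributed dependent variables were analyzed using ttests or ANOVA and non-normally distributed dependent variables were analyzed using Kruskal-Wallis tests". It does not say whether the Aim 2 outcome is the post value or the change, whether the t-tests are paired or unpaired, or which terms the ANOVA contains.

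The SAP's opening paragraph says survey and observational data were aggregated to 85 centers and tested at the 0.05 level. It gives no numbers per arm. Protocol 8.4 says that matched counties, four in all, were the units randomized.

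**The concern.** A paired t-test is a one-sample test on change scores and has no Group term. If the Aim 1 analysis is carried out as written, nothing in it bears on the comparison with control staff, although Group is listed as an independent variable.

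The control arm is what this trial adds. Protocol 8.5 criticizes earlier child care IPM studies for lacking control groups, and Protocol 8.6 already reports an uncontrolled rise in staff knowledge from 61% to 88%. A within-arm test in this trial repeats that kind of evidence. Staff answer a knowledge survey before and after the workshop (Protocol 8.9 and 8.11), so some gain from seeing the questions twice is plausible. The active control could remove that gain, but only if the arms are compared.

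Aim 2 raises a milder question: can a reader tell which contrast supports Hypothesis 2?

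**Working it through.** **Contrasts promised and tests named**

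| Hypothesis | Contrast | Test named in the SAP |
|---|---|---|
| 1 | Against own pre-workshop level | Paired t-test |
| 1 | Against control staff | None |
| 2 | Against own pre-intervention level | t-test, ANOVA or Kruskal-Wallis; contrast not stated |
| 2 | Against control centers | t-test, ANOVA or Kruskal-Wallis; contrast not stated |

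The documents give no power or effect-size figure for Aims 1 and 2, so there is none to reproduce. The size of the problem can only be illustrated.

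**Inputs**
- From the SAP: 85 centers in total, significance level 0.05.
- Assumed: a two-sided test, 42 IPM centers and 43 control centers, normally distributed center-level changes, and centers independent of one another.
- Varied: a shift d, in SDs of change, that both arms share. The true workshop effect is zero throughout.

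**Paired test in the IPM arm**

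The statistic follows a noncentral t distribution with 41 degrees of freedom and noncentrality d × √42, where √42 = 6.481. The two-sided critical value is 2.020.

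| Shared shift d | Noncentrality | Chance of a significant result |
|---|---|---|
| 0.20 | 1.296 | 24.4% |
| 0.33 | 2.160 | 55.9% |
| 0.50 | 3.240 | 88.6% |

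In raw units, a 5-point re-test gain is 0.33 SD if the SD of change is 15 (5/15) and 0.5 SD if it is 10 (5/10). The split hardly matters: with 43 IPM centers the rates at 0.2 and 0.5 SD are 24.9% and 89.3%.

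**Between-arm test of change**

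The shared shift cancels in the difference between arms. In 20,000 simulated trials with a 43/42 split, the two-sample t-test on change was significant in 4.9% to 5.1% at shifts from 0 to 0.8 SD. Kruskal-Wallis on change gave 4.2% to 5.0% in 2,000 trials.

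**Paired tests run separately in both arms**

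Reading the workshop as effective when the IPM arm is significant and the control arm is not gave false success in about 19%, 25% and 10% of trials at shared shifts of 0.2, 0.3 and 0.5 SD. Two within-arm tests therefore do not replace one between-arm test.

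**The case against.** There are several fair points in favor of the plan.

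- **The before-after half of Hypothesis 1 is tested.** Aim 1 as worded in Protocol 8.3 asks only whether the workshop improves knowledge and does not mention controls. This stands, and it limits the finding to the control half. It does not remove it, because Hypothesis 1 states the control comparison outright.
- **The rates are illustrations.** The documents give neither the arm sizes nor the SD of change, and the result depends heavily on the assumed shift. This stands, which is why a range is shown.
- **Not every rival explanation is well grounded.** If the two surveys are close together, secular change is small. The documents describe no selection of low scorers that would produce regression to the mean. This stands too; a re-test effect is the plausible source of a shared shift.
- **These are not the primary analyses.** The SAP gives that role to the tobit models, so less rests on Aims 1 and 2.

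A reader might also infer that Aim 2 never compares arms, that Hypothesis 2 is therefore untested, and that baseline values are thrown away. The documents do not support this. Group and Time are both listed for Aim 2. An unpaired t-test, one-way ANOVA or Kruskal-Wallis test on change scores compares change between arms, as does the group-by-time term of a repeated-measures ANOVA. The SAP does not say that any of these was done, but it does not exclude them. The opening paragraph also provides for propensity-score or double-robust methods if covariates differ at baseline, although it does not say whether baseline outcome values count as covariates.

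For the same reason, no firm precision loss can be claimed for Aim 2. With baseline-to-post correlation ρ, baseline adjustment is worth 1/(1 − ρ²) times as many centers as a post-only test: 1.33 at ρ = 0.5 and 1.96 at ρ = 0.7. Against a change-score test the factor is 2/(1 + ρ): 1.33 and 1.18. Both ρ values are assumed, and the plan does not say which comparison applies.

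**Conclusion.** For Aim 1 the point holds. The phrase "compared to their pre-workshop knowledge and compared to the control center staff" sets two contrasts, and the SAP names a test for the first only. A significant paired t-test cannot support a statement about control staff. If the workshop adds nothing, that test would still be significant in about 24% to 89% of trials at shared shifts of 0.2 to 0.5 SD, against about 5% for a between-arm test of change. These figures assume 42 IPM centers, normal changes and independent centers. The 5% also assumes that change does not vary by county; if it does, a center-level test that ignores county can exceed 5%.

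For Aim 2 the defect is under-specification: the named tests can carry the comparison, but the contrast is not stated.

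The documents do not say whether control staff answered the IPM items at both times. The instrument list in Protocol 8.11 shows one combined IPM and physical activity knowledge survey, which suggests it but does not settle it.

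**What to change.** **Aim 1.** Regress the center-mean post-workshop IPM score on group, adjusting for the center-mean baseline score and cohort. Base any claim against control on the group coefficient and its confidence interval. Keep the paired t-test as a within-arm description. First confirm that control staff answered the IPM items at both times; if they did not, withdraw the between-arm claim from Hypothesis 1.

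**Aim 2.** For each outcome, state one between-arm comparison that uses baseline: either the post value adjusted for baseline or a group-by-time term. For policy and pest counts, a negative binomial or ordinal model with baseline adjustment would serve.

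**County.** For both aims, say how county enters the analysis, or state plainly that center-level inference ignores the unit that was randomized. With four counties this limitation should be reported beside the result.

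**Cost.** SAP wording and re-analysis of data already collected. A between-arm test asks more of the data: with 43 and 42 independent centers it has about 63% power for a difference in change of 0.5 SD and 80% for 0.61 SD, before baseline adjustment and before any loss from clustering by county.
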